6.14.3.7.2. Definitions of Immunogenicity Assessment Periods

Immunogenicity Baseline Observations: Baseline period for immunogenicity assessment for each participant includes all observations up to baseline visit. In instances where multiple baseline observations are collected, to determine participant ADA status the last non-missing immunogenicity assessment up to first administration of study is used to determine treatment-emergent status (see below).

Immunogenicity Postbaseline Period Observations: Postbaseline period observations for each participant include all observations after the first administration of study drug. There are two different periods listed below:

- The planned treatment period is defined as from the first dose of treatment to end of the treatment period
- The entire postbaseline period is defined as from the first dose of treatment to the end of safety follow-up visit or date of study withdrawal

6.14.3.7.3. Definitions of Participant ADA Status

Treatment-emergent (TE) ADA-evaluable participants: a participant with a non-missing baseline ADA result and at least 1 non-missing postbaseline ADA result.

TE ADA-unevaluable participant: any participant who does not meet the evaluable criteria.

Baseline ADA Present (preexisting antibody): ADA detected in a sample collected up to the first dose date and time.

Baseline ADA Not Present: ADA is not detected, and the corresponding PK concentration is missing or below the drug tolerance limit in a sample collected up to the first dose date and time.

Treatment-emergent ADA positive (TE ADA+) participant: an evaluable participant who had a:

- baseline status of ADA Not Present and at least 1 post-baseline status of ADA Present with titer ≥ 2 x minimum required dilution (MRD), where the MRD is the minimum required dilution of the ADA assay or
- baseline and postbaseline status of ADA Present, with the postbaseline titer being 2 dilutions (4-fold) greater than the baseline titer. That is, the participant has baseline status of ADA Present, with titer 1:B, and at least 1 postbaseline status of ADA Present, with titer 1:P, with $P/B \geq 4$.

As shown in [Figure GPHK.6.2](#), a titer is expected when ADA assay result is Detected. On occasion, the corresponding assay cannot be performed, in which case a titer value will be imputed for the purpose of TE ADA determination. A baseline sample with detected ADA and no titer is imputed to be the MRD (1:10) and a post-baseline sample with ADA detected and no titer is imputed to be one dilution above the MRD (1:20).

TE ADA-Inconclusive participant: a TE ADA-evaluable participant is TE ADA Inconclusive if $\geq 20\%$ of the participant's postbaseline samples are ADA Inconclusive and all remaining postbaseline samples are ADA Not Present.

TE ADA-negative (TE ADA-) participant: a TE ADA-evaluable participant is TE ADA- when the participant is not TE ADA+ and not TE ADA Inconclusive.

NAb-positive (NAb+) participant: a participant who is TE ADA+ and has a NAb positive sample in the postbaseline period.

NAb-Inconclusive participant: a participant who is TE ADA+, is not NAb+, and all samples that have TE ADA+ titer have a NAb-Inconclusive sample result.

NAb-negative (NAb-) participant: a participant is not either NAb+ or NAb inconclusive.

Unless specified otherwise, the above-mentioned definitions of NAb are applicable to all NAb analyses, including cross-reactive NAb analyses, and cross-reactive antibodies.

6.14.3.7.4. Analyses to be Performed

The count and proportion of participants who are TE ADA+ will be tabulated by treatment group, where proportion are relative to the number of TE ADA-evaluable participants, as defined above. The tabulation will include the count and proportion of participants with ADA Present at baseline and the count and proportion of TE ADA+ participants exhibiting each type of cross-reactive antibodies and NAb.

This analysis will be performed for

- the planned treatment period
- the entire postbaseline period including safety follow-up.

The cross-reactive NAb will exclude Tier 4c and 4d results but include in silico classification as cross-reactive NAb for summary.

A summary will be provided of the count and percentage of tirzepatide-treated participants experiencing specific TEAE (see [Table GPHK.6.10](#)) by TE ADA status (TE ADA+, TE ADA-, TE ADA Inconclusive) during the planned treatment period. The PT will be ordered by decreasing incidence in TE ADA+ status group.

Table GPHK.6.10. Adverse Events for Analysis with Immunogenicity Results

TEAE category	Criteria
Hypersensitivity reactions	Anaphylaxis SMQ (narrow or algorithm)
	Hypersensitivity SMQ (narrow)
	Angioedema SMQ (narrow)
	Severe Cutaneous Adverse Reaction SMQ (narrow)
Injection site reactions	Injection site reaction HLT
	Infusion site reaction HLT
	Administration site reaction HLT

Abbreviations: HLT = high level term; MedDRA = Medical Dictionary for Regulatory Activity; SMQ = Standardised MedDRA Query; TEAE = treatment-emergent adverse event.

Additional immunogenicity analyses as determined later may be presented. The relationship between antibody titers, the PK parameters, and pharmacodynamics (PD) response to tirzepatide may also be assessed.

Cases of TE ADA that are associated with TEAEs of either severe/serious hypersensitivity or injection site reactions will be classified as AESIs.

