8.2.4.1. Immunogenicity Assessment

Where local regulations and ERBs allow, blood samples for immunogenicity testing will be collected to determine antibody production against tirzepatide as specified in the Schedule of Activities (Section 1.3).

At the visits and times specified in the Schedule of Activities (Section 1.3), venous blood samples will be collected to determine antibody production against tirzepatide. To interpret the results of immunogenicity, a PK sample will be collected at the same time points as the immunogenicity sample. All samples for immunogenicity should be taken predose when applicable and possible. In the event of systemic drug-hypersensitivity reactions (immediate or nonimmediate), additional samples will be collected (including antidrug antibodies [ADAs], PK, and exploratory biomarker samples) as close to the onset of the event as possible, at the resolution of the event, and 30 days following the event. Instructions for the collection and handling of blood samples will be provided by the Sponsor. The actual date and time (24-hour clock time) of each sampling will be recorded. Immunogenicity will be assessed by a validated assay designed to detect ADAs in the presence of tirzepatide at a laboratory approved by the Sponsor. Antibodies may be further characterized and/or evaluated for their ability to neutralize the activity of tirzepatide. Sample collected at Visit 801 or Visit 802 will assess immunogenicity at washout of tirzepatide (5 half-lives post end of treatment).

Samples with tirzepatide ADA detected will be titered and evaluated for their ability to neutralize the activity of assigned treatment (tirzepatide-neutralizing antibodies). Samples with tirzepatide ADA detected will also be tested for cross-reactive binding to native GIP and GLP-1, and if such is detected, then for neutralizing antibodies against native GIP and GLP-1, respectively.

Treatment-emergent ADAs are defined in Section 9.4.6.

Samples will be retained for a maximum of 15 years after the last participant visit, or for a shorter period if local regulations and ERBs allow, at a facility selected by the Sponsor. The duration allows the Sponsor to respond to future regulatory requests related to tirzepatide. Any samples remaining after 15 years will be destroyed.

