ADA Not Present	ADA assay result is Not Detected and drug concentration is at a level that has been demonstrated to not interfere in the ADA detection method (that is, drug concentration is below the assay's drug tolerance level). For participants receiving placebo, drug concentration is not assessed and is assumed to be below the assay's drug tolerance level. If drug concentration was planned but is not available for a treatment-period sample, a Not Detected sample will be declared ADA Not present.
ADA Inconclusive	ADA assay result is Not Detected but drug concentration in the sample is at a level that can cause interference in the ADA detection method.
ADA Missing	ADA sample not drawn, QNS, not tested, etc., causing there to be no laboratory result reported or the result is reported as "no test."

Abbreviations: ADA = anti-drug antibodies; QNS = quantity not sufficient.

All ADA present samples will be evaluated for cross-reactive glucose-dependent insulinotropic polypeptide (GIP), cross-reactive glucagon-like peptide-1 (GLP-1), Nab LY3298176 (LY) on glucose-dependent insulinotropic polypeptide receptor (GIP-R), and Nab LY on glucagon-like peptide-1 receptor (GLP-1R). If cross-reactive GIP is detected, Nab GIP on GIP-R is evaluated. If cross-reactive GLP-1 is detected, Nab GLP on GLP-1R is evaluated ([Figure GPHK.6.2](#)).

Similar terminology to [Table GPHK.6.8](#) applies for each type of cross-reactive and Nab assay. Importantly, each of these are distinct assays and, in general, have different assay operating characteristics.

The following are considered inconclusive for the NAb result:

- NAb LY on GIP-R: if NAb result is not detected, and pharmacokinetic (PK) concentration is \geq drug tolerance limit of the NAb LY on GIP-R assay
- NAb LY on GLP-1R: if NAb result is not detected, and PK concentration is \geq drug tolerance limit of the NAb LY on GLP-1R assay
- NAb GIP on GIP-R: if NAb result is not detected, and PK concentration is \geq drug tolerance limit of the NAb GIP on GIP-R assay
- NAb GLP-1 on GLP-1R: if NAb result is not detected, and PK concentration is \geq drug tolerance limit of the NAb GLP-1 on GLP-1R assay

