To mitigate inconclusive cross-reactive NAb interpretations against nGIP and nGLP-1 due to potential tirzepatide concentrations greater than or equal to the drug tolerance limit of the cross-reactive NAb assays (Tier 4c and 4d, respectively), an *in silico* method utilizing results from Tiers 2b and 2c, Tiers 4a and 4b, and tirzepatide concentrations is introduced. The *in silico* method is outlined in [Table GPHK.6.9](#).

Table GPHK.6.9. In Silico Classification for Cross-Reactive NAB

In Silico Classification	Cross-reactive Binding ADA Result	NAb Result	Circulating Tirzepatide Level (ng/mL)	In Silico Cross-reactive NAB Interpretation
Cross-reactive NAb to nGIP	Tier 2b: "Not Detected"	Tier 4a: "Not Detected" or Tier 4a: "Detected" or N/A or Missing	Any Value or Missing	Not Present
	Tier 2b: "Detected"	Tier 4a: "Not Detected"	<drug tolerance limit of Tier 4a assay	Not Present
	Tier 2b: "Detected"	Tier 4a: "Not Detected"	\geq drug tolerance limit of Tier 4a assay	Inconclusive
	Tier 2b: "Detected"	Tier 4a: "Detected"	<drug tolerance limit of Tier 4a assay	Present
	Tier 2b: "Detected"	Tier 4a: "Detected"	\geq drug tolerance limit of Tier 4a assay	Present
Cross-reactive NAb to nGLP-1	Tier 2c: "Not Detected"	Tier 4b: "Not Detected" or Tier 4b: "Detected" or NA or Missing	Any Value or Missing	Not Present
	Tier 2c: "Detected"	Tier 4b: "Not Detected"	<drug tolerance limit of Tier 4b assay	Not Present

In Silico Classification for Cross-Reactive NAb

In Silico Classification	Cross-reactive Binding ADA Result	NAb Result	Circulating Tirzepatide Level (ng/mL)	In Silico Cross-reactive NAb Interpretation
Cross-reactive NAb to nGLP-1	Tier 2c: "Detected"	Tier 4b: "Not Detected"	≥drug tolerance limit of Tier 4b assay	Inconclusive
	Tier 2c: "Detected"	Tier 4b: "Detected"	<drug tolerance limit of Tier 4b assay	Present
	Tier 2c: "Detected"	Tier 4b: "Detected"	≥drug tolerance limit of Tier 4b assay	Present

Abbreviations: ADA = antidrug antibodies; GIP = glucose-dependent insulinotropic polypeptide; GLP-1 = glucagon-like peptide-1; NAb = neutralizing antibodies; nGIP = native glucose-dependent insulinotropic polypeptide; nGLP-1 = native glucagon-like peptide-1; Tier 2b = cross-reactive ADA to nGIP; Tier 4a = NAb LY (tirzepatide) on GIP receptor; Tier 4b = NAb LY (tirzepatide) on GLP-1 receptor.

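### The cross-reactive NAb summary discards directly Detected Tier 4c/4d results, so a sample positive against native GIP or GLP-1 can be reported as Not Present or Inconclusive

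*SAP*

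**What the plan says.** **Testing.** Protocol 8.2.4.1 tests samples with anti-drug antibodies (ADA) for cross-reactive binding to native GIP and GLP-1 and, "if such is detected, then for neutralizing antibodies against native GIP and GLP-1, respectively". SAP 6.14.3.7.1 sets the same sequence: "If cross-reactive GIP is detected, Nab GIP on GIP-R is evaluated. If cross-reactive GLP-1 is detected, Nab GLP on GLP-1R is evaluated". These direct native-hormone assays are Tier 4c (GIP) and Tier 4d (GLP-1).

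**When a direct result is inconclusive.** SAP 6.14.3.7.1 gives one condition per assay. For native GIP it reads "NAb GIP on GIP-R: if NAb result is not detected, and PK concentration is \geq drug tolerance limit" of that assay; the GLP-1 line is parallel.

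**Why an in silico class exists.** The same section states the purpose: "To mitigate inconclusive cross-reactive NAb interpretations against nGIP and nGLP-1 due to potential tirzepatide concentrations greater than or equal to the drug tolerance limit" of Tiers 4c and 4d. The method is described as "utilizing results from Tiers 2b and 2c, Tiers 4a and 4b, and tirzepatide concentrations is introduced". Tiers 2b and 2c measure cross-reactive binding. Tiers 4a and 4b measure neutralisation of tirzepatide itself; the table footnote says "Tier 4a = NAb LY (tirzepatide) on GIP receptor", and 4b is the GLP-1 receptor counterpart. Tiers 4c and 4d are not inputs.

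**What is summarised.** SAP 6.14.3.7.4 says "The cross-reactive NAb will exclude Tier 4c and 4d results but include in silico classification as cross-reactive NAb for summary". No exception is made for conclusive direct results.

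**The concern.** The stated reason is narrower than the rule. Drug interference explains why a negative direct result at a high tirzepatide concentration should not be trusted. It does not explain setting aside a positive one, and by the SAP's own definition a positive is never inconclusive. The replacement class is inferred from binding plus neutralisation of a different molecule, so it need not agree with the direct measurement.

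At stake is the reported number of participants with antibodies that neutralise their own GIP or GLP-1, a property for which the protocol plans dedicated assays. If a direct positive is relabelled, the summary will not show it, and no listing or separate count of Tier 4c/4d results is committed to elsewhere in the SAP.

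**Working it through.** No sample size, power or alpha calculation applies, and the plan gives no figure to reproduce. The check applies Table GPHK.6.9 to every combination of its inputs and sets the result beside the direct assay. GIP is shown; the GLP-1 rows (2c, 4b, 4d) have the same structure.

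**Step 1: restrict to samples where 4c exists.** Tier 4c is run only when 2b is Detected (SAP 6.14.3.7.1). The table's rows for 2b Not Detected therefore cannot hide a direct positive.

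**Step 2: list the tabulated cells.** With 2b Detected, the table covers 2 results for 4a × 2 concentration bands = 4 cells.

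| 4a | Tirzepatide level vs 4a limit | In silico class | If 4c is Detected |
|---|---|---|---|
| Detected | below | Present | agrees |
| Detected | at or above | Present | agrees |
| Not Detected | below | Not Present | direct positive reported as absent |
| Not Detected | at or above | Inconclusive | direct positive reported as unresolved |

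The class is the same whatever 4c shows, because 4c is not an input. Of the 4 cells, 1 reports a direct positive as Not Present and 1 as Inconclusive. These are counts of table cells, not probabilities. In the fourth row, a method introduced to reduce inconclusive readings produces one where the direct assay had given an answer.

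**Step 3: compare with the direct rule.** Inconclusive requires both Not Detected and drug at or above the assay's limit. A 4c Detected result fails the first condition at any concentration, so the stated reason for the in silico method never applies to it.

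**Step 4: look for gaps.** With 2b Detected and either 4a or the concentration missing, the table has no row, although a 4c result may exist.

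**Step 5: carry to participant level.** SAP 6.14.3.7.3 makes a participant who is treatment-emergent ADA positive (TE ADA+) NAb-positive on one positive postbaseline sample. The participant is NAb-Inconclusive only if every sample with a TE ADA+ titre is inconclusive, and otherwise NAb-negative. These definitions extend to cross-reactive NAb. Suppose no sample is classed Present in silico. The participant is then NAb-negative in either of these cases:

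- the 4c-Detected sample has a TE ADA+ titre and falls in the third row;
- the 4c-Detected sample falls in the fourth row and another sample with a TE ADA+ titre is Not Present.

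**The case against.** **The cell may be empty.** To reach the third row, a sample must neutralise the native hormone yet test Not Detected against tirzepatide at the same receptor, with drug below the 4a (4b) limit. The sponsor may expect this to be rare, and nothing in the documents shows it occurs. This stands as a limit on size. It does not justify the rule: if such samples are rare, keeping them costs almost nothing.

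**The signal is not wholly lost.** The same tabulation counts cross-reactive binding antibodies, the direct assays are still run, and additional immunogenicity analyses are allowed. This is true, but binding is not neutralisation, and the additional analyses are optional.

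**There is no protocol–SAP conflict.** A reader might infer one because the protocol plans the direct tests. Protocol 9.4.6 promises only tabulations of pre-existing and treatment-emergent ADA and leaves details to the SAP. The objection stands: the inconsistency lies within the SAP, between the reason given for the method and the extent of the exclusion.

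**The direct assay is not shown to be the truth.** A reader might also call the opposite case an error, where 2b and 4a are Detected and 4c is Not Detected below its limit but the class is Present. The documents give no performance, concordance or tolerance values for 4c/4d, so that case is open. It is a reason to display such samples, not to reclassify them.

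**Conclusion.** The point holds in a limited form. As written, the SAP can report a sample with a Detected Tier 4c (4d) result as Not Present or Inconclusive, and can count the participant as NAb-negative. This follows from the text alone and rests on no assumed rate.

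How often it happens cannot be determined. A reader might multiply an assumed ADA rate, an assumed binding rate and an assumed discordance to obtain a count of hidden positives. The documents supply none of these, and a general discordance rate would mix both directions of disagreement, so no such count is supported.

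A reader might also infer that this is the leading immunogenicity safety concern. The documents do not rank it so: SAP 6.14.3.7.4 reserves adverse-event-of-special-interest status for TE ADA associated with severe or serious hypersensitivity or injection site reactions. One descriptive safety summary is affected. Efficacy and type 1 error are untouched.

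**What to change.** Amend the sentence in SAP 6.14.3.7.4 along these lines:

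- Cross-reactive NAb to native GIP (GLP-1) is Present when Tier 4c (4d) is Detected, whatever the in silico class.
- In all other cases the Table GPHK.6.9 class is used.
- Counts are shown by source (direct or in silico).
- Samples where the direct and in silico results disagree are listed, including those classed Present in silico with 4c (4d) Not Detected below that assay's tolerance limit.

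While the text is open, state how Table GPHK.6.9 treats binding Detected with 4a (4b) or the tirzepatide concentration missing.

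The cost is SAP wording, one derivation step and one listing. The assays are already planned in Protocol 8.2.4.1 and SAP 6.14.3.7.1, so no new samples or tests are needed. The small downside is that the summary combines two kinds of evidence, which the counts by source keep visible.

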10.3.1.7. Hypersensitivity Events

All allergic or hypersensitivity reactions will be reported by the investigator as either AEs, or if any serious criterion is met, as SAEs.

In the event of suspected drug hypersensitivity reactions (immediate or nonimmediate) in subjects who experience moderate-to-severe injection reactions as assessed by the investigator, unscheduled blood samples will be collected for PK and ADA analyses at the following time points:

- as close as possible to the onset of the event
- at the resolution of the event
- 30 (\pm 3) days following the event.

Additionally, unscheduled serum samples for immune safety laboratory testing (including, but not limited to β tryptase, total IgE, complement, and cytokine panel testing) should also be collected at approximately 60 to 120 minutes and 4 to 6 weeks after the onset of the event in these participants.

Additional data, such as type of reaction and treatment received, will be collected on any AEs or SAEs that the investigator deems related to study drug(s) via the eCRF created for this purpose. Study drug(s) should be temporarily interrupted in any individual suspected of having a severe or serious allergic reaction to study drug(s). Study drug(s) may be restarted when/if it is safe to do so, in the opinion of the investigator.

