10.3.1.8. Injection Site Reactions

Injection site reactions will be collected on the eCRF separate from the hypersensitivity reaction eCRF. At the time of AE occurrence, samples will be collected for measurement of tirzepatide ADA and tirzepatide concentration.

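### Reactions trigger extra antibody samples that count towards antibody status, so the summary of reactions by that status is biased towards an association

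*SAP*

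**What the plan says.** **Extra samples.** For injection site reactions, Protocol 10.3.1.8 states: "At the time of AE occurrence, samples will be collected for measurement of tirzepatide ADA and tirzepatide concentration". It gives no severity limit. Protocol 8.2.4.1 states: "In the event of systemic drug-hypersensitivity reactions (immediate or nonimmediate), additional samples will be collected", drawn "as close to the onset of the event as possible, at the resolution of the event, and 30 days following the event", which makes three. Protocol 10.3.1.7 lists the same three time points ("unscheduled blood samples will be collected for PK and ADA analyses at the following time points") but words the trigger more narrowly, as suspected drug hypersensitivity "in subjects who experience moderate-to-severe injection reactions as assessed by the investigator".

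**Which samples count.** SAP 6.14.3.7.2 states: "Postbaseline period observations for each participant include all observations after the first administration of study drug". Nothing in SAP 6.14.3.7 limits status to scheduled samples, sets event-triggered samples aside, or requires the antibody to precede the reaction. Elsewhere the SAP does make the distinction: Table GPHK.6.2 uses only scheduled visits for mean changes, and 6.14.6 leaves unplanned measurements out of plots.

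**How status is set.** Under SAP 6.14.3.7.3 a participant is TE ADA positive with "baseline status of ADA Not Present and at least 1 post-baseline status of ADA Present with titer" at or above twice the minimum required dilution. A participant with antibodies at baseline qualifies with a single fourfold rise. The Inconclusive class depends on the share of samples that are inconclusive, with a threshold of 20%.

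**The summary.** SAP 6.14.3.7.4 states: "A summary will be provided of the count and percentage of tirzepatide-treated participants experiencing specific TEAE". The events are the hypersensitivity and injection site reactions of Table GPHK.6.10, tabulated by status as TE ADA positive, negative or inconclusive.

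**The concern.** The event being compared causes extra looks at the factor by which it is compared. Because one positive sample is enough, an added sample can move a participant into the positive group but never out of it. Even if antibodies and reactions were unrelated, participants with a reaction would be classed positive more often, given the same scheduled visits.

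An excess of reactions among antibody-positive participants is also the pattern that a real safety signal would show, so the artefact and the signal point the same way. This is the only comparison of reactions by antibody status to which the SAP commits. Further immunogenicity analyses are optional there.

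**Working it through.** The documents give no figure for this summary, so there is nothing to reproduce.

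**From the documents**
- Scheduled on-treatment postbaseline ADA samples, m: 5 to Week 72 (Weeks 4, 12, 24, 48, 72; Protocol 1.3.1), and 4 more (Weeks 98, 124, 150, 176; Protocol 1.3.2), so 9 to Week 176.
- Extra samples, k: 1 for one injection site reaction, 3 for one qualifying hypersensitivity reaction.

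**Assumed**
- No true association.
- TE ADA positive on scheduled samples alone, T: 20% or 50%.
- Within-person correlation between samples, ρ: 0 to 0.8.
- 5% of participants with an event. This affects the incidences but not the odds ratio.

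**Model.** The per-sample chance of a qualifying result is beta-distributed across participants with mean μ and correlation ρ. With a = μ(1−ρ)/ρ and b = (1−μ)(1−ρ)/ρ, the chance of no qualifying result in n samples is the product of (b+i)/(a+b+i) over i = 0 to n−1. At ρ = 0 it is (1−μ)^n. μ is set so that m samples give T. Then P = 1 − (chance of no qualifying result in m+k samples), and the odds ratio is [P/(1−P)] ÷ [T/(1−T)].

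**Worked case (m = 5, T = 20%, ρ = 0).** μ = 1 − 0.8^(1/5) = 0.0436.
- k = 1: P = 1 − 0.8^(6/5) = 0.2349; odds ratio = (0.2349/0.7651)/0.25 = 1.23.
- k = 3: P = 1 − 0.8^(8/5) = 0.3002; odds ratio = (0.3002/0.6998)/0.25 = 1.72.
- Reaction incidence for k = 3 in positives: 0.05×0.3002/(0.05×0.3002 + 0.95×0.20) = 7.3%. In non-positives: 0.05×0.6998/(0.05×0.6998 + 0.95×0.80) = 4.4%. The truth is 5% in both.

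**Odds ratio with no true association, m = 5**

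| T | k | ρ=0 | ρ=0.3 | ρ=0.6 | ρ=0.8 |
|---|---|---|---|---|---|
| 20% | 1 | 1.23 | 1.12 | 1.06 | 1.03 |
| 50% | 1 | 1.30 | 1.14 | 1.08 | 1.04 |
| 20% | 3 | 1.72 | 1.32 | 1.17 | 1.09 |
| 50% | 3 | 2.03 | 1.40 | 1.20 | 1.10 |

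At 50%, three extra samples and ρ = 0, the incidences read 6.6% against 3.4%. At ρ = 0.8 they read 5.2% against 4.8%.

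**To Week 176 (m = 9), three extra samples.** The odds ratio is 1.39 (ρ = 0) to 1.05 (ρ = 0.8) at 20%, and 1.52 to 1.06 at 50%.

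**Limiting case.** At ρ = 1 the odds ratio is 1.00.

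**Scheduled samples only.** With equal attendance k = 0, so P = T and the ratio is 1.00. A simulation of 4 million participants (m = 5, T = 20%, ρ = 0.6, k = 3) gave a risk ratio of 1.16 on all samples and 1.00 on scheduled samples.

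**Inconclusive class.** One inconclusive sample of five is 20%, which meets the threshold. One of six is 16.7%, which makes the participant negative if the other five are ADA Not Present. An extra sample can therefore change this class too.

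**The case against.** - **Persistence and number of samples.** The largest ratio needs three extra samples, 50% positivity and independence between samples from the same person. None of the assumed inputs is in the documents. If antibodies persist, the bias is small. This stands, so only a range can be given. Recurrent injection site reactions work the other way, since each one triggers a sample.
- **Coverage.** Table GPHK.6.10 counts any event matching four hypersensitivity queries, while the triggers cover only systemic reactions (8.2.4.1) or those with moderate-to-severe injection reactions (10.3.1.7). Events that trigger no sample add no bias. This stands. The link is most complete for injection site reactions, where one event adds one sample.
- **Early stopping.** Protocol 7.1 lists significant drug-related hypersensitivity as a possible reason to stop treatment. If scheduled samples are then missed, two scheduled plus three triggered samples make five again and the risk ratio is 1.00. With one plus three it is 0.79 (ρ = 0) or 0.93 (ρ = 0.6), both at 20% positivity. Section 7.1 asks these participants to keep attending, but an offset remains possible. A reader might infer that the summary must show an association; the documents support only a bias in that direction when scheduled sampling is otherwise equal.
- **Assay interference.** Immunogenicity samples are predose where possible, while a sample at onset may follow a dose closely. SAP 6.14.3.7.1 notes that high drug concentration can affect the assay, so a triggered sample may be less likely to read positive. This stands and is not modelled.
- **Transient antibodies.** If short-lived antibodies do cause reactions, scheduled-only status would miss them and understate a real signal. This stands, and it is why the all-sample version should remain.

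**Conclusion.** The concern holds as a bias in a descriptive safety summary. Each step is in the documents: reactions trigger samples, all samples count, one positive is enough, and the same reactions are tabulated by the resulting status. Under the stated assumptions, with five scheduled samples, the odds ratio with no true association is 1.03 to 1.30 for one extra sample and 1.09 to 2.03 for three. The documents do not say where in that range the trial would fall.

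Two stronger readings are not supported. First, a reader might infer that TE ADA incidence by treatment group is materially inflated. With three extra samples in 5% of an arm, five scheduled samples, 50% positivity and ρ = 0, the rise is 0.05 × (67.0% − 50%) = 0.85 percentage points, the largest value over this range. That does not justify redefining it. Second, a reader might infer a false-positive test or a flawed causal claim. SAP 6.14.3.7.4 plans counts and percentages and names neither a test nor a causal estimand for this summary.

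**What to change.** In SAP 6.14.3.7.4:
- Present the Table GPHK.6.10 summary with TE ADA status derived from protocol-scheduled samples only, side by side with the all-sample version.
- For participants with a reaction, state whether the first TE ADA positive sample preceded it.
- Leave TE ADA incidence by treatment group, and the case-level rule that makes TE ADA with severe or serious reactions an event of special interest, on all samples.

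The cost is one more table and a filter on scheduled visits. The scheduled-only version can miss transient antibodies seen only at the reaction, which the all-sample version still shows. It removes the effect of triggered sampling but does not correct for scheduled visits missed after early stopping.
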